9.1.4 Unexpected Adverse Events

An AE or ADR is considered unexpected if it is not listed in the Investigator Brochure or is not listed at the specificity or severity that has been observed and listed in the Investigator

Brochure. Events that are mentioned in the Investigator Brochure (section Reference Safety Information) as occurring with a class of drugs or as anticipated from the pharmacological properties of the drug but are not specifically mentioned as occurring with the particular drug under investigation are considered unexpected. The determination of expectedness is made by the Sponsor on the basis of the IB Reference Safety Information (RSI) section.

9.1.5 Suspected Unexpected Serious Adverse Reaction

A **suspected unexpected serious adverse reaction (SUSAR)** is defined as an adverse reaction that is both unexpected (not consistent with the applicable reference safety information) and also meets the definition of a Serious ADR.

9.1.6 Adverse Events (AEs) of Special Interest (Sight-threatening Events)

The following adverse events are considered to be of Special Interest and by default shall be reported as SAEs (medically important criteria):

- AEs that caused a decrease in visual acuity of >30 ETDRS letters or > +0.6 LogMAR (compared with the last assessment of visual acuity at the last visit) lasting >1 hour
- AEs that caused a decrease in visual acuity to the level of light perception or worse lasting >1 hour
- AEs that required surgical intervention (e.g., conventional surgery, vitreous tap or biopsy with intravitreal injection of anti-infectives, or laser or retinal cryopexy with gas) to prevent permanent loss of sight.
- AEs associated with severe intraocular inflammation (i.e., 4+ anterior chamber cell/flare or 4+ vitritis)
- AEs that can cause retinal vascular occlusion such as intraocular pressure > 40 mmHg.
- AEs that, in the opinion of the Investigator, may require medical intervention to prevent permanent loss of sight.

9.2 MONITORING AND REPORTING ADVERSE EVENTS

Following study informed consent form signature, at each visit, after the patient has had the opportunity to spontaneously mention any problems, the Investigator or appropriate designee should inquire about AEs by asking the standard questions:

- “Have you had any health problems since your last study visit?”
- “Have there been any changes in the medicines you take since your last study visit?”

AEs should be reported for any clinically relevant change in concomitant condition(s) that is the result of an untoward (unfavorable and unintended) change in patient's medical conditions. Changes in any protocol-specific ocular or systemic parameter evaluated during the study are to be reviewed by the Investigator. In addition, the patient's responses to any questionnaire utilized during the study are to be reviewed by the Investigator. Any untoward (unfavorable and unintended) change in a protocol-specific parameter or questionnaire response that is clinically relevant is to be reported as an AE. These clinically relevant changes will be reported regardless of causality.

All AEs should be followed-up to determine the outcome of the reaction.

In order to collect as complete as possible information in the clinical study database, all ADRs and SAEs ongoing at the time the subject's study participation ends should be evaluated within 10 days after the final visit. After this period, all unresolved ADRs and SAEs will be reported as "ongoing" in the eCRF.

9.3 RECORDING ADVERSE EVENTS

AE data should be obtained through observation of the patient, from any information volunteered by the patient, and through patient questioning.

Adverse Events:

All AEs (non-serious and serious) that occur during the course of the study will be recorded in the eCRF. Any pre-existing medical conditions or signs/symptoms present in a patient prior to the start of the study (i.e., before informed consent is signed) should be specified in the dedicated eCRF sections. Subsequent to signing an informed consent form, all untoward medical occurrences that occur during the course of the study must be documented on eCRF. AEs will be collected till the last follow-up visit (week 8).

When possible, signs and symptoms indicating a common underlying pathology should be documented as one comprehensive event. For each recorded event, the AE documentation must include the onset date, outcome, resolution date (if event is resolved), intensity (i.e., severity), any action with study treatment taken as a result of the event, and an assessment of the adverse event relationship to the study treatment.

Serious Adverse Events:

The Investigator must record all SAEs, including sight-threatening events, occurring at any time during the study (after signature of the informed consent) regardless of presumed causal relationship, on the Serious Adverse Event form in the eCRF of the EDC system within 24 hours of learning of the event; information on the SAE must also be recorded on a specific Non-Carbon Repeat SAE form (included in the Investigator's Site File).

9.3.1 Follow-Up of Patients with Adverse Events

The Investigator is responsible for adequate and safe medical care of patients during the trial and for ensuring that appropriate medical care and relevant follow-up procedures are maintained after the trial. All AEs should be followed-up to determine outcome of the reaction or until 10 days after the final visit (EOS or Early Exit Visit). The Investigator should follow-up the event until resolution or stabilization of the condition. It is the Investigator's responsibility to assure that the patients experiencing AEs receive definite treatment for any AE, if required.

If a patient was hospitalized due to a SAE, a copy of the discharge summary is to be forwarded to Dompé as soon as it becomes available. In addition, a letter from the Investigator that

summarizes the events related to the case as well as results of any relevant laboratory tests may also be requested. Further, depending upon the nature of the SAE, Dompé may request copies of applicable segments of the patient's medical records.

For pharmacovigilance purposes, all SAEs should be followed-up in order to elucidate as completely and practically as possible their nature and/or causality until resolution of all queries, clinical recovery is complete, laboratory results have returned to normal, stable condition is reached or the subject is lost to follow-up. Follow-up may therefore continue until after the patient has left the study up to 10 days after his/her discontinuation from the study for unrelated SAEs, and without timelines for related SAEs, unless the patient denies consent.

9.3.2 Relationship of AEs to the Investigational Medicinal Product

The Investigator will assess the relationship between the AE and the IMP, according to the criteria in Table below.

Table 7: Relationship of the Adverse Event to the IMP

Relationship	Description
None (Intercurrent Event)	An event that is not and cannot be related to the Investigational Product, e.g., patient is a passenger in a road traffic accident or surgical intervention performed during the study but planned before patient enrolment into the study.
Unlikely (remote)	Relationship is not likely e.g., a clinical event including laboratory test abnormality with temporal relationship to drug administration which makes a causal relationship improbable and in which other drugs, chemicals or underlying disease provide more plausible explanations
Possible	Relationship may exist, but could have been produced by the patient's condition or treatment or other cause
Probable	Relationship is likely, the AE abates upon discontinuation of Investigational Product and cannot be due to the patient's condition
Highly Probable	Strong relationship, the event abates upon discontinuation of Investigational Product and, if applicable, reappears upon repeated exposure

An adverse drug reaction (ADR) is defined as an adverse experience which is reasonably likely to have been caused by the drug. Events considered "Possible", "Probable" and "Highly Probable" related to the IMP treatment and implying a reasonable possibility, if considered unexpected, will be reported to appropriate Regulatory Authorities by Dompé.

9.3.3 Severity of AEs

The Investigator will grade the severity of any AE using the definitions in the Table below. For each episode, the highest severity grade attained should be reported.

Table 8: Severity of the Adverse Event

Severity	Description
Mild	Grade 1 - Does not interfere with patient's usual function (awareness of symptoms or signs, but easily tolerated [acceptable]).
Moderate	Grade 2 - Interferes to some extent with patient's usual function (enough discomfort to interfere with usual activity [disturbing]).
Severe	Grade 3 - Interferes significantly with patient's usual function (incapacity to work or to do usual activities [unacceptable])

9.4 SERIOUS ADVERSE EVENT REPORTING

9.4.1 Reporting Procedure for Investigators

The Investigator must report all SAEs filling in and signing a SAE Report form, including sight threatening events, regardless of presumed causal relationship, to Dompé Global Pharmacovigilance, Safety and Surveillance Dept and CRO Pharmacovigilance, by e-mail (preferred) or fax immediately, anyway **within 24 hours** of learning of the event. Contact details for SAE reporting are provided below:

CRO Safety reporting

PPD Pharmacovigilance

4-Hour Safety [contact]

Safety Hotline [contact]

Email: [contact]

Dompé Contact Information

Dompé Global Pharmacovigilance, Safety and Surveillance Department

PPD

Dompé Medical Expert

PPD

PPD

Dompé Clinical Operations

PPD

In addition to reporting the SAE to Dompé, the Investigator must also comply with the requirements related to the reporting of SAEs to the IRB/IEC which approved the study. The requirements of IRBs/IECs vary from one IRB/IEC to another; however, as a minimum requirement, the Investigators must promptly report all suspected unexpected serious adverse reaction (SUSAR) to their IRB/IEC.

If assistance is needed with the reporting of a SAE, CRO/Dompé may be contacted at the addresses provided above.

SAEs will be managed directly by the Dompé Pharmacovigilance, Safety and Surveillance department, with CRO support for follow-up requests.

The investigator should also report information on SAEs that continue after the patient has completed his/her participation in the study (whether study completion or withdrawal) unless the patient has withdrawn his/her consent.

Follow-up reports (as many as required) should be completed and faxed/emailed following the same procedure above, marking the SAE form as “follow-up Number XX”.

Whenever more than one SAE is observed, the Investigator should identify which is the primary adverse event, i.e., the most relevant one. If other events are listed in the same report, the Investigator, along with their relatedness to the IMP, should identify which AEs are serious and which are non-serious. In any case, the Investigator is requested to record his/her opinion about the relatedness of the observed event(s) with the IMP.

An assessment of expectedness and causality of each SAE will be performed case by case by Dompé Pharmacovigilance. For SAE reported by the Investigator as not related that is subsequently assessed to be related by Dompé, the Investigator will receive a notification. Depending on the nature and seriousness of the AE, further information, including copies of appropriate medical records of the patient, as well as results of laboratory tests performed will need to be included in the patient's chart. If the patient was hospitalized, a copy of the discharge summary should be available, if possible.

In line with CT3 Detailed Guidance and ICH E2A provisions, although the Investigator does not usually need to actively monitor patients for AEs once the trial has ended, if the Investigator becomes aware of a SAE occurring to a patient after that patient has ended his/her

participation in the study (whether study completion or withdrawal), the SAE should be reported by the Investigator to the Dompé Pharmacovigilance. Such “post-study cases” should be regarded for expedited reporting purposes as though they were study reports. Therefore, a causality assessment and determination of expectedness are needed for a decision on whether or not expedited reporting is required.

9.4.2 Conditions that should not be reported as Serious Adverse Events

The conditions listed below, that may require hospitalization of a patient, are not considered to be SAE and shall not be reported as such, but only need to be recorded in the eCRF:

- Hospitalizations planned before entry into the clinical study which is part of the normal treatment or monitoring of the studied indication and not associated with any deterioration in condition.
- Hospitalization for routine treatment or monitoring of the studied indication, not associated with any deterioration in condition.
- Hospitalization for treatments, which was elective or pre-planned, for a pre-existing condition that is unrelated to the indication under study and did not worsen.
- Hospitalization for general care not associated with any deterioration in condition.
- Treatment on an emergency, outpatient basis for an event not fulfilling any of the definitions of SAEs given above and not resulting in hospital admission.

In addition, the following situation shall not be considered SAE:

- Abnormal test results that do not induce clinical signs and/or symptoms and do not require intervention/therapy, i.e., are not clinically significant.

9.4.3 Adverse Events Exemption

There are no adverse event exemptions for this study.

9.4.4 Reporting Procedure to IRB/IEC and to Regulatory Authorities

During the course of the clinical trial, the Sponsor shall report any SUSAR to the concerned Regulatory Authority(ies) and IRBs/IEC(s), as soon as possible and in no event later than:

- a) seven calendar days after becoming aware of the information if the event is fatal or life threatening; to be followed by any relevant information within eight days.
- b) fifteen calendar days after becoming aware of the information if the event is neither fatal nor life threatening.

Follow-up information shall be reported within the same timelines.

If the results of an investigation show that an ADR not initially determined to be reportable is reclassified as reportable, the Sponsor shall report such SUSAR in a written safety report as soon as possible, but in no event later than 7/15 calendar days after the determination is made.

Treatment will be unmasked by Sponsor Pharmacovigilance prior to regulatory submission of a SUSAR to Regulatory Authorities and IRBs/IECs and only cases referred to active treatment will be considered expeditable for regulatory reporting, in line with law

requirements.

The Sponsor shall also inform worldwide Regulatory Authorities of SUSARs, as applicable (cross reporting).

Dompé shall also notify FDA in an IND safety report of potential serious risks, from clinical trials or any other source, as soon as possible after Dompé determines that the information qualifies for reporting, in particular shall notify of:

- any suspected adverse reaction that is both serious and unexpected. Dompé must report an adverse event as a suspected adverse reaction only if there is evidence to suggest a causal relationship between the drug and the adverse event.
- findings from other studies that suggest a significant risk in humans exposed to the drug. Such a finding would result in a safety-related change in the overall conduct of the clinical investigation.
- findings from animal or in vitro testing that suggest a significant risk in humans exposed to the drug.
- increased rate of occurrence of serious suspected adverse reactions.

In line with provisions set forth in 21CFR312, Dompé shall notify all participating US Investigators in an IND safety report of any SUSAR and of potential serious risks, from clinical trials or any other source, as soon as possible, but in no case later than:

- Seven calendar days after becoming aware of the information if the event is fatal or life threatening; to be followed by any relevant information within eight days.
- Fifteen calendar days after becoming aware of the information if the event is serious but neither fatal nor life threatening.

The Investigators in turn shall notify their IRB/IEC.

Copies of all correspondence relating to reporting of any SAEs to the IRB/IEC should be maintained in the Investigator's Files.

According to US regulations, the Investigators will be informed in an unmasked manner: Dompé will open the masking and report only SUSAR referred to rhNGF ophthalmic solution.

EU Investigators shall be informed periodically, in a masked fashion, in line with applicable requirements.

As part of periodical information, the Sponsor shall notify the Investigator on a six-monthly basis of any serious ADRs (maintaining the masked condition) that occur during ongoing clinical trials.

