Number of Patients	
Two hundred and ninety-one (291, 97 per group) male or female patients need to be randomized in a 1:1:1 ratio to have at least 276 evaluable patients (92 per group). Patients randomized to the vehicle arm will be randomly assigned 1:1 to two different vehicle filling volumes, namely 1 mL or 2 mL of diluent, to preserve masking. The total number has been obtained considering a 5% rate of patients not evaluable for primary analysis after enrollment. Considering a screen failure rate of 20%, approximately 350 subjects need to be screened in order to have 291

Information	Description
	patients enrolled.

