
Information	Description
	
not an exclusion criterion but must be removed and discontinued at the screening visit).
 
17. Medical history of drug addiction or alcohol abuse (>1 drink /day for women and >2 drinks /day for men following USDA dietary Guidelines 2020-2025).
 
18. Any prior ocular surgery including but not limited to amniotic membrane transplant, refractive (PTK/LASIK/Epi-LASIK/LASEK/SMILE), palpebral, cataract surgery, trabeculectomy, vitrectomy and pan-retinal photocoagulation (PRP) within 90 days before the screening visit.
 
19. Participation in a clinical trial with a new active substance, including medical devices, during the previous 60 days.
 
20. Participation in another clinical trial study at the same time as the present study.

Study Medication, Dosage and Mode of Administration	
The route of administration for the study products is ophthalmic with the administration applied in both eyes.
 
The IMPs consist in a new formulation to be reconstituted daily by the patients (kit containing CCI rhNGF + diluent for reconstitution) for topical ocular administration at the following concentrations of active ingredient:
 
 IMP 1: rhNGF C mcg/mL IMP 2: rhNGF C mcg/mL IMP (vehicle): rhNGF 0 mcg/mL 
During the treatment period, the IMPs are administered according to the following scheme:
 
 - IMP 1: One drop of rhNGF C mcg/mL instilled in both eyes TID (every approx. 6 hours). - IMP 2: One drop of rhNGF C mcg/mL instilled in both eyes TID (every approx. 6 hours). - IMP (vehicle): One drop of Vehicle instilled in both eyes TID (every approx. 6 hours). 
A bi-weekly kit will be provided to the patient at the time of baseline (visit 2) and week 2 (visit 3) visits. An ancillary kit containing sterile pipettes for vials adapter and sterile wipes will be provided at the same time. In addition to that, for the Run-In period a bi-weekly kit of vehicle will be given to the patients, and for all the Follow-Up period the Sponsor will also supply preservative free artificial tears (AT).

Duration of Treatment	
Four (4) weeks (28 Days±1) of treatment with IMPs according to the randomization list.

Primary Efficacy Endpoint	
The primary efficacy endpoint is the mean change from baseline to Week 8 in symptoms of dry eye assessed by SANDE Global Score [Time Frame: week 8 (V5)].

Information	Description

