2.2 NAME AND DESCRIPTION OF THE INVESTIGATIONAL MEDICINAL PRODUCT

Recombinant hNGF, the active principle, has the same sequence of native hNGF. The cGMP grade investigational medicinal product (IMP) consists of a CCI product comprising recombinant human nerve growth factor (rhNGF, C mcg/vial), CCI CCI dissolved in 1 mL (IMP2) or 2 mL (IMP1) of a diluent containing CCI CCI. The vehicle solution contains the same CCI preparation without rhNGF, and it is dissolved in 1 mL or 2 mL of the same diluent to ensure the study masking. The reconstitution of the CCI product with the diluent yields in all cases a sterile aqueous solution suitable for ophthalmic use (eye drops). For more information see §6.1.

The vehicle solution is used during the Run-In period by all eligible patients for 12±2 days, as described in §6, and the same vehicle is administered to the IMP (vehicle) group for 4 weeks between visit 2 and visit 4. IMP1 is the ophthalmic solution containing C mcg/mL of rhNGF while IMP2 is the ophthalmic solution containing C mcg/mL of rhNGF. These solutions (and the components) are indicated in this study with the general name of Study Product(s).

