2.3.2 Toxicology Studies

The ocular tolerance and potential toxicity of the new formulation containing the test item rhNGF (recombinant human nerve growth factor) and the new excipient, CCI was assessed following daily administrations by the ocular topical route (eye drops, 3 times a day in both eyes, 4-hour apart) for at least 13 weeks in the New-Zealand White rabbits and the reversibility of any findings was evaluated during a 2-week recovery period. In addition, a proof of exposure of the compounds was determined.

Animals were administered with rhNGF at C or at C µg/day or vehicle (Reconstitution Solvent containing the new excipient CCI eye drops, three times a day, in both eyes for at least 13 weeks. The following parameters and end points were evaluated: Mortality, clinical observations, body weights and body weight gains, food consumption, ophthalmology evaluation, including modified Mac Donald - Shadduck examination with detailed ophthalmic examination, tonometry and esthesiometry, clinical pathology parameters (hematology and clinical chemistry), proof of exposure, organ weights, macroscopic and microscopic examinations.

No rhNGF or CCI level was determined in the respective analyzed serum samples. This lack of systemic absorption after the topical ocular administration of rhNGF was expected.

During the in-life phase, rhNGF, formulated in CCI did not cause any mortality or clinical signs. There were neither test item-related changes in body weight nor in food consumption. There were no rhNGF formulation-related ophthalmic findings for both dose levels at all evaluated examinations or measurements during the dosing period. No ophthalmic findings were detected in the control animals treated with the formulation vehicle containing CCI. No treatment-related changes in clinical pathology parameters were observed.

The pathology evaluation did not reveal any test item-related changes in organ weight or test item-related findings at macroscopic and microscopic examinations.

In conclusion, under the study experimental conditions, daily ocular topical administration of

rhNGF at C or C µg/day to the New-Zealand White rabbit for at least 13 weeks was well tolerated during the in-life phase and did not cause clinical signs, clinical pathology and organ weights changes, gross and microscopic findings. As expected after ocular administration by eye drops, no systemic exposure to rhNGF or CCI was detected.

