This is the first study with a new formulation of the rhNGF eye drops	rhNGF eye drop formulation at C mcg/mL has been already tested in patients and it is currently marketed (over 16000 patients exposed so far). In this study a new formulation at C mcg/mL and at C mcg/mL will be tested to evaluate safety, efficacy, and tolerability.	In previous studies rhNGF was used at the concentration of C mcg/mL. No difference in safety and possibly a reduction of CCI and CCI is expected with the use of the new formulation, especially considering the CCI in rhNGF concentration. Patients with known allergy to any component of the new formulation will be excluded from participating in the study. AE information and VBR10 data will be collected throughout the study including the Run-In and follow-up period (Visit 2).
Adherence to treatment with vehicle/IMPs/NIMP in the Run-In period, treatment period and Follow-Up period, respectively	During the different phases of the study (Run-In, treatment, Follow-Up), the accountability and the adherence to the specific treatments that will be supplied by the Sponsor should be registered and evaluated	Adherence to the use of the treatments is to be monitored via Patient Diaries implemented for each study period to register the administration of the vehicle (Run-In period), the IMPs/vehicle (treatment period) and preservative free AT (NIMP in Follow-Up period). The Patient Diary will be evaluated to define the adherence to the treatments. A site visit (Visit 3) is programmed after 2 weeks of treatment to check the Patient Diary for medication dosing compliance. The Study Products and AT will be dispensed in controlled amounts at specific visits and used/unused study products will be collected during the successive visits. A check of the returned Study Product vehicle from the Run-In period and IMP or vehicle will be done at every visit starting from visit 2 by independent personnel not directly involved in study activities.
IMP Preparation and storage	New formulation of Study Products to be reconstituted by the Patients (kit containing CCI + diluent) Storage temperature	Instruction for reconstitution will be provided to patients. First vehicle administration during the Run-In period will be performed at the site with the support of clinical staff to show patient reconstitution and administration system. A

Potential Risk of Clinical Significance	Summary of Data/Rationale for Risk	Mitigation Strategy

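### Section 9.4.4 limits expedited SUSAR reports to active-treatment cases, against its own opening rule and although the vehicle carries the new excipient

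*Protocol*

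**What the plan says.** On reporting, the Protocol makes these statements:

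- Section 9.4.4 opens by saying that the sponsor reports any SUSAR to authorities and IRBs/IECs, within 7 calendar days if fatal or life-threatening and within 15 otherwise.
- Section 9.3.2 says that unexpected events with a possible or stronger relationship to IMP treatment go to the authorities.
- Section 9.4.4 then says that the sponsor unmasks before submission and that "only cases referred to active treatment will be considered expeditable for regulatory reporting", adding that this follows the law.
- For US investigators, Section 9.4.4 promises notice of any SUSAR on the same 7/15-day clock, and later states: "Dompé will open the masking and report only SUSAR referred to rhNGF ophthalmic solution".
- EU investigators are told periodically and in masked form, with six-monthly notice of serious ADRs.

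On the product:

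- The first risk in Table 2 (Section 2.7) is: "This is the first study with a new formulation of the rhNGF eye drops".
- Section 2.3.2 describes the "new formulation containing the test item rhNGF (recombinant human nerve growth factor) and the new excipient", and says that the vehicle used in the rabbits contained that excipient.
- Section 2.2 says that the clinical vehicle is the same preparation and diluent without rhNGF. The Synopsis and Section 6.3 list the vehicle among the IMPs, and SAP Section 3.4 counts it as study treatment.
- "The vehicle solution is used during the Run-In period by all eligible patients for 12±2 days", and "the same vehicle is administered to the IMP (vehicle) group for 4 weeks between visit 2 and visit 4".

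**The concern.** An active-only filter is reasonable when the comparator is inert and familiar. Here the familiar component is rhNGF, which is marketed with over 16,000 patients exposed (Section 2), and the new component is the formulation with its excipient. A serious, unexpected reaction to that excipient in a patient on vehicle bears on every patient in the two rhNGF arms, because they receive the same base. It also fits the Protocol's own SUSAR definition (Section 9.1.5), since the vehicle is an IMP. The restricting sentences would nevertheless take such a case off the sponsor's fast route. Run-in is each patient's first contact with the new base, and all of it is on vehicle.

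**Working it through.** **1. Follow one case through the text.** Take a serious, unexpected reaction judged related to the excipient in a vehicle-arm patient.

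- Section 9.1.5: a SUSAR.
- Section 9.3.2: reportable to authorities, because the vehicle is an IMP.
- Section 9.4.4, opening: reportable to authorities and IRBs/IECs in 7 or 15 days.
- Section 9.4.4, restriction: after unmasking, not expeditable.
- Section 9.4.4, US investigators: due under the any-SUSAR sentence, not sent under the rhNGF-only sentence.

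Two of the statements that govern the sponsor's report exclude the case and the others include it. The restrictions are the more specific sentences, so they are the ones likely to be followed. For the same case in run-in there is nothing to unmask, and Section 9.4.4 does not mention run-in. Read literally, a run-in patient is not on active treatment and is excluded, but that is an inference.

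**2. Planned numbers.** The documents give no exposure share, so the sample size is reproduced first. Inputs (Section 10.1): difference 28.2 − 17.4 = 10.8, SDs 26.36 and 20.29, one-sided alpha 0.0125, power 80% for one comparison.

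- Normal approximation: (26.36² + 20.29²) × (2.2414 + 0.8416)² / 10.8² = 90.2, so 91 per group.
- Unequal-variance t calculation: 92 per group (power 80.2%), which is the plan's figure.
- With 5% not evaluable: 92 / 0.95 = 96.8, so 97 per group; 276 / 0.95 = 290.5, so 291. The plan agrees: "Two hundred and ninety-one (291, 97 per group) male or female patients need to be randomized in a 1:1:1 ratio".

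**3. Exposure to the new base, in patient-days.** Run-in is 12 days (10 to 14). Treatment: "Four (4) weeks (28 Days±1) of treatment with IMPs according to the randomization list". Dosing frequency is the same in both periods, so shares in drops are the same.

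- Run-in on vehicle: 291 × 12 = 3,492
- Vehicle arm: 97 × 28 = 2,716
- All vehicle: 6,208
- Active arms: 194 × 28 = 5,432
- Vehicle share: 6,208 / 11,640 = 53.3%

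Range over the visit windows:

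- Run-in 10 days, treatment 29 days: 5,723 / 11,349 = 50.4%
- Run-in 14 days, treatment 27 days: 6,693 / 11,931 = 56.1%

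The share passes one half when 291r + 97T > 194T, that is, when r > T/3. For T = 29 this is 9.67 days, below the shortest permitted run-in of 10.

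If all 350 − 291 = 59 screened but not randomised patients completed run-in (an assumed upper bound), the share is (350 × 12 + 2,716) / (6,916 + 5,432) = 6,916 / 12,348 = 56.0%.

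**4. Same question, other denominators.**

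- Patients who never receive active drug: 97 / 291 = 33.3%.
- Treatment period only: 2,716 / (291 × 28) = 33.3%.
- Vehicle arm alone as a share of all patient-days, if the filter does not reach run-in: 2,716 / 11,640 = 23.3%.

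**The case against.** The strongest reply is that a vehicle case is not lost.

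- Every SAE goes to the sponsor within 24 hours whatever its presumed cause, and sponsor pharmacovigilance judges causality and expectedness case by case (Section 9.4.1). Sight-threatening events are SAEs by default (Section 9.1.6).
- Investigators must promptly report all SUSARs to their own IRB/IEC (Section 9.4.1). Sections 11.1 and 12.2 add further notices to IRBs/IECs, none limited by arm.
- Section 9.4.4 also provides for telling the FDA and US investigators of potential serious risks, which could capture some vehicle cases. The periodic reports remain (Sections 9.4.4 and 9.4.5).
- Thirteen weeks of rabbit dosing gave no ophthalmic findings on vehicle (Section 2.3.2), and patients with known or suspected allergy to a component are excluded (Section 5.2). Few events are expected.
- Excipient reactions in the active arms would be expedited.
- The clause cites the law, and what the law requires cannot be settled from these documents.

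All of this stands, and it lowers the severity. It does not remove the explicit active-only sentences or their conflict with Section 9.3.2 and the opening of Section 9.4.4. The potential-serious-risk clause is worded around the drug, so its reach to the vehicle is unclear. A legal minimum would not stop the sponsor from reporting more.

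**Conclusion.** The point holds as an internal contradiction with a safety consequence. Followed as written, the restriction takes SUSARs attributable to the vehicle or its excipient off the sponsor's 7/15-day report to authorities, IRBs/IECs and US investigators. Vehicle makes up about 53% of planned patient-days on the new base (50% to 56% across the windows) if run-in is counted, or 33% of patients and of treatment-period exposure. This assumes that the clinical vehicle contains the excipient named in the toxicology section, which Section 2.2 supports, and that planned durations are met. The percentage describes exposure, not missed reports. No endpoint or efficacy analysis is affected.

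A reader might infer more than the documents support:

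- *EU investigators would wait six months because of this rule.* Their notice is periodic and masked for active cases too, so the rule causes no EU-specific delay.
- *IRBs/IECs would hear only of active cases.* Investigators must still report all SUSARs to their own committee.
- *Run-in cases are expressly excluded.* Section 9.4.4 does not mention run-in, and the restriction follows from a step about unmasking.
- *Most patients fall outside expedited reporting.* The majority is of patient-days and depends on run-in.
- *Without a DMC nobody would see the case.* The sponsor sees it within 24 hours.
- *The rule breaks the law.* The documents cannot show this either way.

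**What to change.** Reconcile Sections 9.3.2 and 9.4.4. Replace the two active-only sentences so that a SUSAR reasonably attributable to the vehicle or any excipient follows the same 7/15-day route to authorities, IRBs/IECs and US investigators as an rhNGF case. State explicitly that this covers both the vehicle arm and run-in, and that run-in cases need no unmasking because every run-in patient is on vehicle. State that causality is assessed against the Study Product, vehicle included. Settle the form of the US notice at the same time, because Section 6.4.3 says that unmasked information is not disclosed to investigators while Section 9.4.4 informs US investigators unmasked.

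The cost is a wording change in the Protocol and matching safety procedures, plus at most a few extra expedited reports and unmaskings by pharmacovigilance. Section 6.4.3 already has pharmacovigilance unmask any SAE that meets SUSAR criteria, so the extra unmasking should be small. No visits, data or sample size change.
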